4.3 TREATMENT COMPLIANCE

BI 754111 and BI 754091 will be administered by i.v. infusion at the sites by the Investigator and/or trained site personnel, and dosing will be recorded in the eCRF. Therefore, actual dosing is expected to precisely follow the prescribed drug regimen. Missed or interrupted doses will be recorded in the eCRF with the associated reasons. The method of collecting dosing information assures that total exposure can be calculated programmatically taking into account any missing doses.

5. ASSESSMENTS

5.1 ASSESSMENT OF EFFICACY

The treatment efficacy will be assessed according to RECIST Version 1.1 ([R09-0262](#)) and iRECIST ([R17-0923](#)) for the evaluation of the tumor response in patients with solid tumors. An overview of iRECIST will be found in [Appendix 10.3](#).

The assessment by the Investigator and/or the local radiologist will be the basis for continuation or discontinuation of the trial in an individual patient (in addition to safety). The baseline imaging must have been performed within 4 weeks prior to start with anti-LAG-3 treatment BI 754111 and the Investigator will record the target and non-target lesions in the eCRF. The same method of assessment and the same technique must be used to characterise each reported lesion at baseline and during treatment. Lesions in previously irradiated areas may not be considered measurable at baseline unless the lesions occurred after irradiation. The baseline tumor assessment will be performed as close as possible (and no more than 28 days) to the start of the anti-LAG-3 treatment BI 754111 (i.e. within the week before Cycle1 Visit1 or during Cycle 1). Further assessments will be performed every 2 Cycles during the first 6 months and at the EOT visit (if not performed within the last 4 weeks). Following 6 months of treatment, tumor assessments can be done once every 3Cycles, and at the discretion of the Investigator.

Following PD, a patient may continue to receive treatment for a maximum of a year if the Investigator, Medical Monitor, and sponsor agree that the patient is deriving clinical benefit.

Copies of CT/ Magnetic Resonance Imaging (MRI)/PET scan data will be collected by the sponsor for later radiomics assessment. It is planned to explore the potential for enhanced and improved baseline and on-treatment markers/ patterns of early efficacy based on comprehensive quantitative CT metrics, i.e. radiomics features, assessed in standard-of-care medical imaging data.

5.2 ASSESSMENT OF SAFETY

5.2.1 Physical examination

A complete physical examination will be performed at the time points specified in the Flow Chart. It includes at a minimum general appearance, neck, lungs, cardiovascular system, abdomen, extremities, and skin.

Measurement of height and body weight will be performed at the time points specified in the [Flow Chart](#).

The results must be included in the source documents available at the site.

5.2.2 Vital signs

Vital signs will be evaluated at the time points specified in the [Flow Chart](#), prior to blood sampling.

This includes systolic and diastolic blood pressure and pulse rate (electronically or by palpation count for 1 minute) in a seated position after 5 minutes of rest. The results must be included in the source documents available at the site.

5.2.3 Safety laboratory parameters

Blood (venous) samples will be collected at the times indicated in the [Flow Chart](#) and will be analysed by the sites' local safety laboratories. Screening laboratory assessments performed within 72 hours of the first trial treatment administration are not required to be repeated on Cycle 1 Day 1. In cases where screening laboratory investigations have been performed >72 hours prior to the first trial treatment intake, the results of the new laboratory investigations performed within 72 hours of the first trial treatment administration must be available to confirm eligibility.

The tests to be performed are described in [Table 5.2.3: 1](#).

Table 5.2.3: 1 Safety laboratory tests

Hematology	Red blood cell count, haemoglobin, haematocrit, mean corpuscular volume, white blood cell count, and differential blood count will be expressed in absolute values, and platelets will be measured
Biochemistry	Standard safety panel: glucose, sodium, potassium, chloride, calcium, phosphate, venous bicarbonate HCO ₃ , creatinine, creatinine phosphokinase (CPK), AST, ALT, alkaline phosphatase, lactate dehydrogenase (LDH), bilirubin, total protein, albumin, urea nitrogen (or urea), uric acid and troponin
	Baseline additional panel then when clinically indicated: cholesterol, triglycerides, c-peptide, and creatine phosphokinase
	In case of pathological creatine phosphokinase: CPK-MB, additional troponin I and myoglobin should be reactively tested and the findings documented
	Thyroid panel (TSH, free T4, and free T3): at the time of each standard biochemistry panel
	To be analysed in case of symptoms of pancreatitis: amylase and lipase
Urinalysis	Urine (pH, glucose, erythrocytes, leukocytes, protein, and nitrite) will be analysed by dipstick (semi-quantitative measurements) during the screening visit, at the EOT visit, and as clinically indicated. In case of pathological findings, further evaluation must be performed and the findings documented
Pregnancy test	Beta human chorionic gonadotropin (β-HCG) pregnancy test in urine or serum will be performed for women of childbearing potential at screening, within 14 days prior to first trial treatment, on Day 1 of each cycle prior to administration of the treatment drug(s), before the start of each repeated cycle, and at the EOT visit.

In case the criteria for hepatic injury are fulfilled, a number of additional measures will be performed (please see [Section 5.2.6.1.4](#) and the Potential DILI Checklist provided in the ISF). The amount of blood taken from the patient concerned will be increased due to this additional sampling.

5.2.4 **Electrocardiogram**

The 12-lead ECGs must be administered by a qualified technologist and results will be recorded as scheduled in the [Flow Chart](#). The investigator or a designee will evaluate whether the ECG is normal or abnormal and whether it is clinically relevant, if abnormal. ECGs may be repeated for quality reasons and the repeated recording used for analysis.

Additional ECGs may be recorded for safety reasons. Dated and signed printouts of ECG with findings should be documented in patient's medical record.

Clinically relevant abnormal findings will be reported either as baseline condition (if identified at the screening visit) or otherwise as adverse events and will be followed up and/or treated as medically appropriate.

5.2.5 **Other safety parameters**

Not applicable

5.2.6 **Assessment of adverse events**

5.2.6.1 Definitions of AEs

5.2.6.1.1 Adverse event

An AE is defined as any untoward medical occurrence in a patient or clinical investigation subject administered a medicinal product and which does not necessarily have to have a causal relationship with this treatment.

An AE can therefore be any unfavourable and unintended sign (including an abnormal laboratory finding), symptom, or disease temporally associated with the use of a medicinal product, whether or not considered related to the medicinal product.

5.2.6.1.2 Serious adverse event

A serious adverse event (SAE) is defined as any AE which fulfils at least one of the following criteria:

- results in death,
- is life-threatening, which refers to an event in which the patient was at risk of death at the time of the event; it does not refer to an event that hypothetically might have caused death if more severe.
- requires inpatient hospitalisation or
- requires prolongation of existing hospitalisation,
- results in persistent or significant disability or incapacity, or
- is a congenital anomaly/birth defect, or
- is deemed serious for any other reason if it is an important medical event when based on appropriate medical judgement which may jeopardise the patient and may require medical or surgical intervention to prevent one of the other outcomes listed in the above definitions. Examples of such events are intensive treatment in an emergency room or at home for allergic bronchospasm, blood dyscrasias or convulsions that do not result in hospitalisation or development of dependency or abuse.

Patients may be hospitalised for administrative reasons during the trial, including hospitalisation for respite care. These as well as hospitalisations/surgical procedures which were planned before the patient signed informed consent need not be reported as SAEs if they have been documented at or before signing of the informed consent and have been performed as planned (the condition requiring hospitalisation/surgical procedure has not changed/worsened after signing informed consent).

5.2.6.1.3 AEs considered “Always Serious”

Every new occurrence of cancer of new histology must be classified as a serious event regardless of the duration between discontinuation of the trial medication and must be reported as described in [Section 5.2.6.2](#), subsections “AE Collection” and **AE reporting to sponsor and timelines**”.

In accordance with the European Medicines Agency initiative on Important Medical Events, BI has set up a list of further AEs, which by their nature, can always be considered to be “serious” even though they may not have met the criteria of an SAE as defined above. The latest list of “Always Serious AEs” can be found in the electronic Data Capture (eDC) system. These events should always be reported as SAEs as described above.

5.2.6.1.4 Adverse events of special interest (AESIs)

The term AESI relates to any specific AE that has been identified at the project level as being of Particular concern for prospective safety monitoring and safety assessment within this trial, e.g. the potential for AEs based on knowledge from other compounds in the same class. AESIs need to be reported to the sponsor’s Pharmacovigilance DePartment within the same timeframe that applies to SAEs, please see above.

The following are considered as AESIs: irAEs, infusion-related AEs, potential DILI events, and hepatic injury are AESIs (see below).

Immune-related adverse events (irAEs)

Immune-related AEs are AEs associated with immunotherapy treatments that appear to be associated with the immune therapy’s mechanism of action. These adverse reactions, which can be severe, may involve the gastrointestinal, skin, liver, endocrine, respiratory, renal, or other organ systems. All immune-relate events are to be reported as AEs. Some irAEs also need to be reported as AESIs as defined by the sponsor in [Table 10.1: 1](#). If an Investigator determines a grade 3 event (not on the list) to be immune-related, the Investigator should also report that event as an AESI.

Recommendations for the management of irAEs are presented in [Appendix 10.2](#).

Infusion-related reactions

To reduce the risk of IRRs, patients are to be pre-treated with an antihistamine and acetaminophen or paracetamol. Pre-treatment should be administered at sufficient time prior to initiation of infusion to allow the agents to exert their effect.

In the event of an infusion-related reaction ≤ Grade 2, treat the symptoms accordingly with antihistamine or corticosteroids if needed, the infusion rate of BI 754111 and/or the

Proprietary confidential information © 2020 Boehringer Ingelheim International GmbH or one or more of its affiliated companies

combination of BI 754111 plus BI 754091 may be decreased by 50% or interrupted until resolution of the event and re-initiated at 50% of the initial rate until completion of the infusion. In patients experiencing infusion-related reactions \leq Grade 2, subsequent infusions may be administered at 50% of the initial rate. *If an infusion related reaction is Grade 3 or higher in severity at any point during the study, permanently discontinue study drug(s).*

If a patient experiences an infusion-related reaction, acetaminophen and/or an antihistamine (e.g., diphenhydramine) and/or corticosteroid or equivalent medication per institutional standard may be administered prior to subsequent infusions at the discretion of the Investigator for secondary prophylaxis of infusion-related reactions. If an infusion-related reaction is Grade 3 or higher in severity at any point during the study, treatment with BI 754111 and BI 754091 will be permanently discontinued for the patient.

As with any mAb, allergic reactions to dose administration are possible. Appropriate drugs and medical equipment to treat acute anaphylactic reactions must be immediately available, and trial personnel must be trained to recognise and treat anaphylaxis. The trial site must have immediate access to emergency resuscitation teams and equipment in addition to the ability to admit patients to an intensive care unit if necessary.

The following terms describe those events that are to be considered potential infusion-related AEs. Regardless of grade, these events are considered as AESIs and must be reported to the Sponsor within 24 hours of the event:

- Allergic reaction
- Anaphylaxis
- Cytokine-release syndrome
- Serum sickness
- Infusion reactions
- Infusion-like reactions

If the Investigator determines that another event (not on the list) may be a potential infusion-related AE, the Investigator may also report that event as an AESI

Hepatic injury and potential drug-induced liver injury (DILI)

During the course of the trial the investigator will remain vigilant for increases in liver biochemistry. The investigator is responsible for determining whether a patient meets the hepatic injury definition or potential Hy's Law criteria at any point during the trial.

The investigator participates, together with BI clinical project representatives, in review and assessment of cases meeting potential hepatic injury and Hy's Law criteria. Hy's Law criteria are met if there is no alternative explanation for the elevations in liver biochemistry other than a DILI caused by the investigational product.

The investigator is responsible for recording data pertaining to these cases and for reporting them as AEs and/or SAE according to the outcome of the review and assessment in line with standard safety reporting processes.

Hepatic injury definition:

[figure not shown]
In patient with normal baseline hepatic function, hepatic injury is defined by the following alterations of hepatic laboratory parameters:

- an elevation of AST and/or ALT ≥ 3 fold ULN combined with an elevation of total bilirubin ≥ 2 fold ULN measured in the same blood draw sample, and/or
- *Mark peak ALT, and/or AST elevation ≥ 10 fold ULN*

These lab findings constitute a hepatic injury alert and the patients showing these lab abnormalities need to be followed up according to the “DILI checklist” provided in the ISF. In case of clinical symptoms of hepatic injury (icterus, unexplained encephalopathy, unexplained coagulopathy, right upper quadrant abdominal pain, etc.) without lab results (ALT, AST, total bilirubin) available, the investigator should make sure these parameters are analysed, if necessary in an unscheduled blood test. Should the results meet the criteria of hepatic injury alert, the procedures described in the DILI checklist should be followed.

Lab values meeting this definition of hepatic injury will need to be reported as an AESI. Please follow the flowchart below for reporting hepatic injury / potential DILI cases.

Processing Potential DILI Cases in Oncology

* Such as PD, viral hepatitis, and etc.

** Report as AESI even if PD is determined (PD exemption does not apply for Potential DILI cases)

*** Mark on DILI checklist that hepatic injury is due to a non-DILI etiology, such as PD, and submit DILI checklist & supporting source documents with SAE form

Figure 5.2.6.1.4: 1 Processing of potential DILI cases

Hy's Law cases have the following 3 components:

- *The drug causes hepatocellular injury, generally shown by a higher incidence of 3-fold or greater elevations above the ULN of ALT or AST*
- *Among trial subjects showing such aminotransferase elevations, often with elevations much greater than 3 times ULN, one or more show elevation of serum total bilirubin to > 2 times ULN, without initial findings of cholestasis (elevated serum ALP)*
- *No other reason can be found to explain the combination of increased aminotransferase and total bilirubin, such as hepatitis A, B, or C; preexisting or acute liver disease, or another drug capable of causing the observed injury.*

5.2.6.1.5 Intensity (severity) of AEs

The intensity (severity) of AEs should be classified and recorded in the eCRF according to the CTCAE Version 5.0.

5.2.6.1.6 Causal relationship of AEs

Medical judgement should be used to determine the relationship, considering all relevant factors, including pattern of reaction, temporal relationship, de-challenge or re-challenge, confounding factors such as concomitant medication, concomitant diseases and relevant history.

Arguments that may suggest that there is a reasonable possibility of a causal relationship could be:

- The event is consistent with the known pharmacology of the drug.
- The event is known to be caused by or attributed to the drug class.
- A plausible time to onset of the event relative to the time of drug exposure.
- Evidence that the event is reproducible when the drug is re-introduced
- No medically sound alternative aetiologies that could explain the event (e.g. pre-existing or concomitant diseases, or co-medications).
- The event is typically drug-related and infrequent in the general population not exposed to drugs (e.g. Stevens-Johnson syndrome).
- An indication of dose-response (i.e. greater effect size if the dose is increased, smaller effect size if dose is diminished).

Arguments that may suggest that there is no reasonable possibility of a causal relationship could be:

- No plausible time to onset of the event relative to the time of drug exposure is evident (e.g. pre-treatment cases, diagnosis of cancer or chronic disease within days/weeks of drug administration; an allergic reaction weeks after discontinuation of the drug concerned)
- Continuation of the event despite the withdrawal of the medication, taking into account the pharmacological properties of the compound (e.g. after 5 half-lives).
- Of note, this criterion may not be applicable to events whose time course is prolonged despite removing the original trigger.
- Additional arguments amongst those stated before, like alternative explanation (e.g. situations where other drugs or underlying diseases appear to provide a more likely explanation for the observed event than the drug concerned).
- Disappearance of the event even though the trial drug treatment continues or remains unchanged.

5.2.6.2 Adverse event collection and reporting

5.2.6.2.1 AE Collection

The investigator shall maintain and keep detailed records of all AEs in the patient files. The following must be collected and documented on the appropriate CRF(s) by the investigator:

- From signing the informed consent onwards until the end of treatment (including the safety Follow-up period, a period of 30 days after the last dose of trial medication): all AEs (serious and non-serious) and all AESIs.
- After the individual patient's end of trial: the investigator does not need to actively monitor the patient for AEs but should only report any occurrence of cancer of new histology, related SAEs and related AESIs of which the investigator may become aware of by any means of communication, e.g. phone call. Those AEs should however, not be reported in the CRF.

The rules for Adverse Event Reporting exemptions still apply.

5.2.6.2.2 AE reporting to sponsor and timelines

The investigator must report SAEs, AESIs, and non-serious AEs which are relevant for the reported SAE or AESI, on the BI SAE form immediately (within 24 hours) to the sponsor's unique entry point (country specific contact details will be provided in the ISF). The same timeline applies if follow-up information becomes available. In specific occasions, the investigator could inform the sponsor upfront via telephone. This does not replace the requirement to complete and fax the BI SAE form.

With receipt of any further information to these events, a follow-up SAE form has to be provided. For follow-up information the same rules and timeline apply as for initial information.

5.2.6.2.3 Information required

For each AE, the investigator should provide the information requested on the appropriate eCRF pages and the BI SAE form. The investigator should determine the causal relationship to the trial compounds.

The following should also be recorded as an (S)AE in the CRF and BI SAE form (if applicable):

- Worsening of pre-existing conditions other than the underlying disease
- Changes in vital signs, ECG, physical examination and laboratory test results, if they are judged clinically relevant by the investigator.

If such abnormalities already pre-exist prior to trial inclusion they will be considered as baseline conditions and should be collected in the eCRF only.

All (S)AEs, including those persisting after individual patient's end of trial must be followed up until they have resolved, have been assessed as "chronic" or "stable", or no further information can be obtained.

5.2.6.2.4 Pregnancy

In rare cases, pregnancy might occur in a clinical trial. Once a patient has been enrolled in the clinical trial and has taken trial medication, the investigator must report any drug exposure during pregnancy in a trial Participant immediately (within 24 hours) by means of Part A of the Pregnancy Monitoring Form to the sponsor's unique entry point.

The outcome of the pregnancy associated with the drug exposure during pregnancy must be followed up and reported to the sponsor's unique entry point on the Pregnancy Monitoring Form for Clinical Trials (Part B).

The ISF will contain the Pregnancy Monitoring Form for Clinical Trials (Part A and B).

As pregnancy itself is not to be reported as an AE, in the absence of an accompanying SAE and/or AESI, only the Pregnancy Monitoring Form for Clinical Trials and not the SAE form is to be completed. If there is an SAE and/or AESI associated with the pregnancy an SAE form must be completed in addition.

5.2.6.2.5 Exemptions to SAE reporting

Protocol specified outcome events should be collected on the appropriate CRF page only.

Disease progression is a trial endpoint for analysis of efficacy and as such is exempted from reporting as an AE or an SAE. Progression of the subject's underlying malignancy will be recorded on the appropriate pages of the eCRF as Part of efficacy data collection only and will not be reported on the SAE Form. It will therefore not be entered in the safety database (ARISg) and hence not get expeditiously reported. Death due to disease progression is also to be recorded on the appropriate eCRF page and not on the SAE Form.

However, when there is evidence suggesting a causal relationship between the study drug(s) and the progression of the underlying malignancy, the event must be reported as an SAE on the SAE Form and on the eCRF.

Examples of exempted events of PD may be:

- Progression of underlying malignancy (PD): if PD is clearly consistent with the suspected progression of the underlying malignancy as defined by the respective response criteria.
- Hospitalisation/procedures due solely to the progression of underlying malignancy (PD)
- Clinical symptoms and/or signs of progression (without confirmation by objective criteria e.g., imaging, clinical measurement): if the symptom can exclusively be determined to be due to the progression/relapse of the underlying malignancy and does not meet the expected pattern of progression for the disease under study.

Exempted events are collected and tracked following a protocol specified monitoring plan. Exempted events are monitored at appropriate intervals throughout the study.

Lab values meeting the hepatic injury definition as defined in [Section 5.2.6.1.4](#) will need to be reported as AESI. PD reporting exemption does not apply to hepatic injury.

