7.3 PLANNED ANALYSES

All individual data will be listed. Adherence to the protocol will be checked. Important protocol violations (IPVs) will be identified no later than in the Report Planning Meeting and provided in the trial statistical analysis plan (TSAP).

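### The third example of events exempt from SAE reporting (Protocol 5.2.6.2.5) has its pattern condition pointing the opposite way to the first; a minor wording fix is needed

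*Protocol*

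**What the plan says.** The general rule in Protocol 5.2.6.2.5 is: "Disease progression is a trial endpoint for analysis of efficacy and as such is exempted from reporting as an AE or an SAE". Such events go on the efficacy pages of the eCRF, not on the SAE form. They therefore do not reach the safety database and are not reported in an expedited way.

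Three examples follow, introduced as events that may be exempt:

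- **First:** progression of the malignancy, "if PD is clearly consistent with the suspected progression of the underlying malignancy as defined by the respective response criteria".
- **Second:** hospital stays or procedures caused by progression alone, with no condition on pattern.
- **Third:** clinical symptoms or signs of progression that have not been confirmed by imaging or measurement, "if the symptom can exclusively be determined to be due to the progression/relapse of the underlying malignancy" and if it "does not meet the expected pattern of progression for the disease under study".

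Two limits apply. An SAE must be reported "when there is evidence suggesting a causal relationship between the study drug(s) and the progression of the underlying malignancy". In addition, "PD reporting exemption does not apply to hepatic injury". The section also states: "Exempted events are collected and tracked following a protocol specified monitoring plan".

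**The concern.** The third example covers the events with the weakest evidence, because nothing objective supports the diagnosis of progression. For these one would expect a fit with the usual course of the disease to count in favour of exemption. The text makes the absence of that fit a condition for it.

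This matters because the trial combines two checkpoint inhibitors. Protocol 1.4 lists pneumonitis among the immune-related events of the class and mentions rare fatal colitis and pneumonitis, and patients with lung cancer are enrolled. Appendix 10.3 warns that apparent growth under immunotherapy need not be true progression. An unusual, unconfirmed deterioration is therefore one where a drug effect could be taken for tumour. An investigator following the example literally could record it as efficacy data only. It would then be absent from the safety database and from the patient-based AE and SAE tables in SAP 7.8.1.

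**Working it through.** No arithmetic applies. The check is a logical reading of the third example, compared with the neighbouring text.

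**Step 1. What the third example covers.** Its two conditions are joined by *and*. For an unconfirmed symptom:

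| Attributed exclusively to tumour | Fits expected pattern | Named as exempt, as worded | Named as exempt, negation deleted |
|---|---|---|---|
| yes | yes | no | yes |
| yes | no | yes | no |
| no | yes | no | no |
| no | no | no | no |

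As worded, the only case named is the atypical one. Deleting the negation swaps the first two rows and changes nothing else.

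**Step 2. Comparison with the first example.** That example exempts an event because it is consistent with progression under the response criteria. The third exempts an event that departs from the expected pattern. The event classes differ (criteria-defined progression against unconfirmed symptoms), so both can be applied without logical conflict. Their direction is opposite.

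**Step 3. Comparison with the attribution condition.** Protocol 5.2.6.1.6 lists the pattern of a reaction among the factors for judging causality. That rule concerns relationship to study drug, so it bears on attribution to tumour only by analogy. The reasoning carries over: with neither objective confirmation nor a fit to the usual pattern, little is left to support an exclusive attribution. An atypical symptom can still be caused by tumour, so this is a tension in the evidence and not a contradiction.

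**Step 4. Does other text settle it?** The rest of the protocol and the SAP neither restate nor correct the example, and neither defines the expected pattern. The log for Global Amendment 2 explains its clarification of this section by the hepatic-injury carve-out and does not mention the pattern condition.

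**Step 5. Do the two limits cure it?** Only in part. The causality limit concerns a link between drug and progression, so it does not address a non-tumour event wrongly labelled as progression. The hepatic limit covers liver laboratory findings only.

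**Step 6. Size.** The documents give no event rate for unconfirmed clinical progression and no final number treated. No expected count or change in an SAE percentage can be derived.

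**The case against.** The strongest reply is that exclusive attribution already protects against the feared case. If an atypical picture casts doubt on a tumour cause, the event fails that condition and is reportable. The list is also only illustrative, and the general rule exempts true progression whatever the third example says. These points stand, and they limit how much the wording can change.

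Other safeguards also stand:

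- SAP 7.8.1 summarises all deaths by primary cause, including death due to disease.
- The SMC reviews both safety and efficacy data (Protocol 8.7).
- Clinically relevant changes in vital signs, ECG, examination and laboratory results are still to be recorded as adverse events (Protocol 5.2.6.2.3).
- Exempted events are tracked, although the monitoring plan is not in the text available, so its quality cannot be judged.

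A reader might infer that the first and third examples flatly contradict each other, or that the protocol sets out to hide atypical events. The documents support neither: the examples concern different event classes, and the wording looks like a slip, though nothing proves it.

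What the objection does not answer is why the specific example for unconfirmed symptoms, the one an investigator would consult, should name the atypical case and omit the typical one.

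**Conclusion.** The point holds as a minor inconsistency of wording in an operative safety-reporting rule. The third example runs against the direction of the first and sits poorly with its own attribution condition. Its possible consequence is the loss of an occasional atypical, unconfirmed event from the safety database and the AE and SAE tables. This rests on an investigator reading the example literally and having already attributed the event to tumour alone.

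It would be tempting to conclude that the trial's SAE rates are materially understated. The documents do not support that, because nothing indicates how many such events occurred. The primary SUV endpoint is not touched.

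A separate and smaller point concerns AESIs. The catch-all for immune-related events not on the list says Grade 3, in both Protocol 5.2.6.1.4 and Table 10.1: 1, while other entries in that table say Grade 3 or above. One might infer that more severe off-list events go unreported. That does not follow: they remain AEs, fatal or life-threatening events are SAEs with the same 24-hour timeline, and SAP 7.8.1 tabulates immune-related events by highest grade over the whole trial.

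**What to change.** 1. In Protocol 5.2.6.2.5, reconcile the third example with the first. The simplest way is to change *does not meet* to *does meet*, so that an atypical unconfirmed symptom is no longer given as an example of an exempt event. No further exemption rule is needed. Cost: a few words, and slightly more SAE forms.

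2. SAP section 4 says the sponsor ended the trial early, and the documents do not say whether patients remained on treatment, so a change of wording may have little effect from here on. If database lock has not occurred and the eCRF records the basis for progression, review the events recorded as clinical progression without objective confirmation. The last report planning meeting before lock (SAP 6.2) is a suitable place. Protocol 7.3 already promises that "All individual data will be listed", but the documents do not show an eCRF field that separates unconfirmed from confirmed progression, so this step is conditional. Cost: one listing to review.

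3. Reconcile the catch-all grade in Protocol 5.2.6.1.4 and Table 10.1: 1 with the wording used elsewhere in that table. Cost: a few words in two places, and possibly a few more AESI reports.
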